4.3 Screen Failures

Screen failures are defined as patients who consent to participate in the clinical study but are not subsequently entered in the study. Individuals who do not meet the criteria for participation in this study (screen failure) may be rescreened.

4.4 Patient Discontinuation of Treatment or Study Completion/Withdrawal

Patients will be informed before study entry that they are free to discontinue study treatment and to withdraw from the study treatment at any time and for any reason. Patients will also be informed that, if they withdraw, they can ask the Investigator to destroy any identifiable samples taken from them.

4.4.1 Patient Discontinuation of Study Treatment

Study treatment will be discontinued in any of the following occurrences:

- Progressive disease. If the patient is experiencing overall clinical benefit, the patient may be allowed to remain on the study. Both the Medical Monitor and the Investigator must agree that this is appropriate for the patient.
- Unmanageable toxicity.
- Request for early discontinuation or withdrawal of consent by the patient.
- The Investigator decides it is in the patient's best interest to discontinue treatment and/or participation in the study. Reasons may include the following:
 - The patient requires prohibited medications or initiates treatment with another drug for treating prostate cancer
 - The patient is not adherent to the protocol

If a patient discontinues CORT125281, enzalutamide will be continued per the guidelines provided in Section 5.7.1.1. If a patient discontinues enzalutamide, CORT125281 will also be discontinued.

Patients who discontinue study treatment for reasons other than withdrawal of consent (eg, AE, Investigator decision) will undergo a Post-Treatment/ EOT Visit and EOT +30 Days Visit, and will be followed for progression and survival.

4.4.2 Patient Withdrawal from Study/Study Completion

Withdrawal from the study (including all follow-up assessments) will occur under the following circumstances:

- Withdrawal of consent for follow-up observation by the patient
- Patient is lost to follow-up
- Study termination by Sponsor
- Death

If a patient withdraws from the study, the Investigator should complete and report the observations as thoroughly as possible up to the date of withdrawal and the primary reason for withdrawal. For patients who withdraw consent to participate in the study, every effort should be made to determine whether the withdrawal of consent was related to an AE or a specific aspect of the study.

The Investigator will ask all withdrawn patients to consent to a follow-up examination, to check that they have come to no harm as a result of taking part in the study. Provided that patients agree, they will undergo the standard medical examination and laboratory tests that they would have undergone had they completed it.

If a patient withdraws from the study without meeting study endpoints, the Investigator will immediately (within 48 hours after discontinuation) notify the Sponsor.

4.5 Restrictions During the Study

If a patient engages in sexual intercourse with a woman of childbearing potential, a condom with spermicide and another form of birth control must be used during and for 100 days after the final dose of study treatment with (CORT125281 or enzalutamide, whichever is later). The following are acceptable forms of contraception (to be used with a condom with spermicide):

- Established use of oral, injected or implanted hormonal methods of contraception
- Placement of an intrauterine device or intrauterine system
- Barrier methods of contraception: occlusive cap (diaphragm or cervical/vault caps) with spermicidal foam/gel/film/cream/suppository
- Tubal ligation
- Vasectomy or other surgical castration prior to initial Screening

A condom is required during and for 100 days after treatment with enzalutamide if a patient is engaged in sexual activity with a pregnant woman. Patients must also agree to avoid sperm donation during the study and for at least 100 days after the final treatment administration.

5 STUDY TREATMENTS AND MANAGEMENT

Study drug is defined as CORT125281. The co-administered drug is defined as enzalutamide.

Study treatment is defined as CORT125281 and/or enzalutamide, administered according to the protocol.

5.1 Study Drug (CORT125281) and Placebo

CORT125281 and placebo appearance, dose strength (active), administration, packaging, labeling, and storage, are described in Table 1. The starting dose of CORT125281 is described in Section 1.5.2.

Table 1 Study Drug and Placebo: Formulation, Administration, Packaging, and Storage

Specifications	Study Drug and Placebo	
	CORT125281	Placebo
Description	
 • CORT125281 hard-shell capsules, 20 mg and 60 mg • CORT125281 softgel capsules, 40 mg 	Placebo for CORT125281 softgel capsule
Supplied/Unit Dose Strength	CORT125281 hard-shell capsules: Two strengths of study drug will be provided as banded, hard-shell gelatin capsules: 
 • 20 mg (White, Size 3 capsule) • 60 mg (White, Size 0 capsule) 	Not applicable (no hard-shell gelatin placebo)
	CORT125281 softgel capsules: One strength of study drug will be provided as softgel capsules: 
 • 40 mg (Opaque brown, oval softgel capsule) 
NOTE: Existing patients currently administered CORT125281 20-mg and 60-mg hard-shell gelatin capsules will continue with their dosing until their supply of hard-shell gelatin capsules are depleted; at that time the patient will be switched to CORT125281 40-mg softgel capsules at similar doses/exposures to their currently tolerated dose, or per the recommended Phase 2 regimen.
	Placebo for CORT125281 40-mg softgel capsule matches the appearance of the CORT125281 40-mg softgel capsules.
Administration	Oral Swallow capsules whole. Do not chew, dissolve, or open the capsules.	Oral Swallow capsules whole. Do not chew, dissolve, or open the capsules.

Specifications	Study Drug and Placebo	
	CORT125281	Placebo
Packaging and labeling	
CORT125281 20-mg and 60-mg hard-shell capsules will be provided in bottles containing 30 capsules.
 
CORT125281 40-mg softgel capsules will be provided in:
 
 • Bottles with open label containing 30 capsules • Bottles with blinded labels containing 21 capsules 	
Placebo for CORT125281 40-mg capsules will be provided in bottles with blinded labels containing 21 capsules.

Storage	
Store as follows:
 
 • In a secure location • At 20°C to 25°C (68°F to 77°F) with excursions allowed between 15°C and 30°C (59°F and 86°F) • Out of reach and sight of children 	
Store as follows:
 
 • In a secure location • At 20°C to 25°C (68°F to 77°F) with excursions allowed between 15°C and 30°C (59°F and 86°F) • Out of reach and sight of children
Packager	Corcept Therapeutics	Corcept Therapeutics

5.2 Non-Investigational Medicinal Agent (Enzalutamide)

Enzalutamide description, packaging, and storage are described in [Table 2](#). The starting dose of enzalutamide is described in [Section 1.5.2](#).

Table 2 Enzalutamide: Formulation, Administration, Packaging, and Storage

Specifications	Enzalutamide (Xtandi®) ^a
Description	Xtandi® (enzalutamide) capsule
Supplied	White to off-white oblong soft gelatin capsules imprinted with black ink with “ENZ”
Unit dose strength	40 mg enzalutamide/capsule
Dose levels	
 • Dose-Determination Phase Segment 1: Starting dose of 160 mg QD, with subsequent dosing to be determined based upon PK • Dose-Determination Phase Segment 2: At the patient’s currently tolerated dose at baseline • Expansion Phase: 160 mg QD if not currently receiving enzalutamide or at the patient’s currently tolerated dose at baseline if ongoing from the immediately preceding line of therapy
Administration	
Oral
 
Swallow capsules whole. Do not chew, dissolve, or open the capsules.

Packaging and labeling	Commercially available enzalutamide, 40 mg capsules will be provided by the site in bottles containing 120 capsules

Specifications	Enzalutamide (Xtandi®) ^a
Storage	Store as follows: 
 • In a secure location • In their original bottles • At 20°C to 25°C (68°F to 77°F), in a dry place, tightly closed. Excursions will be permitted from 15°C to 30°C (59°F to 86°F) • Keep this and all medications out of the reach of children
Packager	Astellas Pharma US Inc.

5.3 Timing of Study Treatment Administration

5.3.1 Dose-Determination Phase Segment 1 (Twice-Daily Dosing of CORT125281)

Patients in Dose-Determination Phase Segment 1 will take CORT125281 BID beginning on Cycle 1 Day 1 (every 12 hours \pm 3 hours) unless otherwise specified ([Table 3](#)), with the first dose occurring in the morning. It is recommended that if a patient misses a scheduled dose of CORT125281 and less than 6 hours have passed since the scheduled dosing time, the dose should be taken immediately. It is recommended that if more than 6 hours have passed since the scheduled dosing time, the patient should not take the missed dose, but should wait and take the next regularly scheduled dose. A window of at least 6 hours should be maintained between doses.

Alternative dosing schedules for CORT125281 dosing may be evaluated. If alternative schedules are evaluated, the total daily dose of CORT125281 will not exceed that projected to provide an exposure (AUC_{0-24} and C_{max}) of 1.5-fold the previous dose level.

Enzalutamide will be taken once a day, starting on Day -28 (Lead-In Period) and continuing through the combination period ([Table 3](#)) and, unless otherwise specified, should be taken in the morning. After completion of Cycle 2, enzalutamide may be dosed in the evening, if preferred by the patient or recommended by the Investigator.

The treatment schema for Dose-Determination Phase Segment 1 is summarized in [Table 3](#).

Table 3 Treatment Schema for Dose-Determination Phase Segment 1

Cycle Study Treatment	Lead-In Period	Combination Treatment Period
	Days –28 to –1	Days 1 to 28
Cycle 1 CORT125281 Enzalutamide	No dose taken Once a day	Twice a day Once a day
Cycle 2 – End CORT125281 Enzalutamide	N/A N/A	Twice a day Once a day

N/A, not applicable.

5.3.2 Dose-Determination Phase Segment 2 (Once-Daily Dosing of CORT125281)

Patients in Dose-Determination Phase Segment 2 will take CORT125281 QD beginning on Cycle 1 Day 1 and enzalutamide QD (continuing from the previous regimen). CORT125281 should be taken with the evening meal, unless otherwise specified for PK/PD assessments. The window between CORT125281 doses should be ≥ 18 hours from the previous dose. Patients participating in this part of the study will not have a Lead-In Period.

To help ensure ≥ 18 hours from the previous CORT125281 dose are maintained between doses and to allow PK/PD assessments to be taken in the clinic during normal hours, [Table 4](#) provides recommended dosing times. After Cycle 2, all doses of CORT125281 should be taken in the evening around the same time each day, with the evening meal. Enzalutamide should be taken once a day at a consistent time of day (the time of day is per the Investigator's discretion).

Table 4 Example Treatment Times for Dose-Determination Phase Segment 2

Day	CORT125281 Administration					
	Cycle 1		Cycle 2		Cycle 3 and Subsequent Cycles	
	Example Dosing Time	Time Since Prior Dose	Example Dosing Time	Time Since Prior Dose	Example Dosing Time	Time Since Prior Dose
1 ^a	10:00-12:00	N/A	11:00-12:00	18 h	Any time in the evening with the evening meal	≥ 18 h
2-13	18:00	24-32 h	18:00	24-31 h		
14	17:00-18:00	23-24 h	17:00-18:00	23-24 h		
15 ^a	11:00-12:00	18 h	11:00-12:00	18 h		
16-27	18:00	24-31h	18:00	24-31 h		
28	17:00-18:00	23-24 h	17:00-18:00	23-24 h		

h, hour; N/A, not applicable; QD, once daily.

Note: Time of administration is displayed in international format. The example times are provided as a suggestion but may not match the actual dosing times, as long as CORT125281 is always administered with at least 18 hours between each once-daily dose. Thus, on days with PK/PD assessments, dosing may occur in the morning so long as an 18-hour window is maintained.

^a Both CORT125281 and enzalutamide will be administered in the clinic on this day, at the same time, if PK/PD assessments will be collected.

5.3.3 Expansion Phase

In the Expansion Phase Food-Effect Subcohort, patients will receive a single dose of CORT125281 under fasting conditions on Cycle 1 Day -7 (Lead-In Period), and a single dose of CORT125281 30 minutes after a standard breakfast on Cycle 1 Day 1. After this, patients will be treated with CORT125281 BID and enzalutamide QD for the remainder of the Combination Treatment Period.

The treatment schema for patients in the Food-Effect Subcohort of the Expansion Phase is summarized in [Table 5](#).

Table 5 Treatment Schema for Expansion Phase: Food-Effect Subcohort

Cycle Study Treatment	Lead-In Period		Combination Treatment Period	
	Day -7	Day -6 to Day -1	Day 1	Days 2 to 28
Cycle 1 CORT125281 Enzalutamide	Single morning dose No dose taken	No dose taken No dose taken	Single morning dose No dose taken	Twice a day Once a day
Cycle 2 – End CORT125281 Enzalutamide	N/A N/A	N/A N/A	Twice a day Once a day	Twice a day Once a day

N/A, not applicable.

Patients who are not in the Food Effect Subcohort will not have a Lead-In Period. These patients will initiate treatment with both CORT125281 BID and enzalutamide QD on Cycle 1 Day 1.

The treatment schema for non-food-effect patients in the Expansion Phase is summarized in [Table 6](#).

Table 6 Treatment Schema for Expansion Phase: Non-Food-Effect Patients

Cycle Study Treatment	Combination Treatment Period
	Days 1 to 28
Cycle-1 - End CORT125281 Enzalutamide	Twice a day Once a day

N/A, not applicable.

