- **Expansion Phase (Phase 2a, CORT125281 at the RD Under Fed Conditions):** Once the RD has been determined in the Dose-Determination Phase, the following cohorts will be enrolled and treated with CORT125281 (with the RD regimen, under fed conditions) + enzalutamide. The DRC may elect to expand more than 1 dose level, if needed, to better define the RD:
 - Abiraterone (Abi)-Resistant Cohort: Patients who have progressed during treatment with abiraterone and no other AR-blocking therapies
 - Androgen-Receptor (AR) Antagonist (ARant)-Resistant Cohort: Patients who have progressed during treatment with enzalutamide or second-generation AR-blocking therapies

The overall study design is presented in [Figure S1](#).

Figure S1 CORT125281-601 Phase 1/2a Schematic:

AR, androgen receptor; BID, twice daily; DLT, dose-limiting toxicity; DRC, Data Review Committee; MTD, maximum tolerated dose; PD, pharmacodynamic; PK, pharmacokinetic; QD, once daily.

^a. The DRC will review the safety, PK, and PD data from Dose-Determination Segment 1 once a minimum of 3 evaluable patients have completed the DLT-evaluation period (Section 5.4.1).

^b. Enzalutamide will be continued at the dose currently tolerated by the patient at the time of Screening.

^c. The investigational agent will be increased in 40-mg increments every 2 weeks, as tolerated, with either CORT125281 to a maximum dose of 320 mg QD under fed conditions (Arm A) or with placebo (Arm B) to maintain a CORT125281 dose of 240 mg QD under fed conditions (Table S1).

^d. After the DRC meeting for Dose-Determination Segment 2 and determination of the Phase 2 RD, patients initially randomized to Arm B will have their CORT125281 dose escalated per the recommended Phase 2 regimen.

Patients will participate in the following study periods:

- **Screening Period** will take place within 28 days before the first dose of study treatment
- **Lead-In Period:**
 - Dose-Determination Phase Segment 1: Enzalutamide monotherapy for 28 days
 - Dose-Determination Phase Segment 2: No Lead-In Period
 - Expansion Phase:
 - Food-Effect Subcohort only: A single dose of CORT125281 under fasting conditions on Cycle 1 Day -7, and a single dose of CORT125281 30 minutes after a standard breakfast on Cycle 1 Day 1
 - Non-Food-Effect Patients: No Lead-In Period

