- Dose-Determination Phase Segment 2: CORT125281 starting dose of 240 mg QD (softgel capsules, with food), with titration of CORT125281 (Arm A) or placebo (Arm B). CORT125281 should be taken with the evening meal, unless otherwise specified.
- Expansion Phase: CORT125281 at the RD, as determined in the Dose-Determination Phase

Mode of Administration: Oral

Reference Product, Dose, and Mode of Administration (Dose-Determination Phase Segment 2 Only)

Formulation: Placebo softgel capsules to match the appearance of the CORT125281 softgel (40 mg) capsules

Dose: No active (CORT125281) ingredient (0 mg)

Mode of Administration: Oral

Enzalutamide Dose and Mode of Administration

Formulation: Enzalutamide capsules, 40 mg

Dose:

- Dose-Determination Phase Segment 1: Enzalutamide at the starting dose of 160 mg QD, with subsequent dosing to be determined based upon PK
- Dose-Determination Phase Segment 2: Enzalutamide at the patient's currently tolerated dose at baseline. Enzalutamide should be taken once a day (the time of day is per the Investigator's discretion, except where noted for days with PK/PD sample collections).
- Expansion Phase: Enzalutamide 160 mg QD if not currently receiving enzalutamide or at the patient's currently tolerated dose at baseline if ongoing from the immediately preceding line of therapy

Mode of Administration: Oral

Criteria for Evaluation

The SoAs are provided in [Appendix A](#).

Efficacy Assessments

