Once both segments of the Dose-Determination Phase are complete, and the RD has been determined, patients will be enrolled into expanded safety cohorts to further evaluate the safety, tolerability, preliminary efficacy, and PK of CORT125281 in combination with enzalutamide and exploratory biomarkers of sensitivity or resistance. Based on the hypothesis that GR activation compensates for diminished AR signaling in CRPC treated with enzalutamide and facilitates cancer cell survival; the expansion cohorts will include:

- Abiraterone (Abi)-Resistant Cohort: Patients who have previously progressed while receiving abiraterone
- AR Antagonist (ARant)-Resistant Cohort: Patients who have previously progressed while receiving enzalutamide or other second-generation AR inhibitors.

The effect of food on CORT125281 PK will be assessed in 10 patients enrolled in the Expansion Phase. The expansion cohorts will be enrolled in parallel.

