3.1.2 Expansion Phase (Phase 2a)

Once the RD has been determined in the Dose-Determination Phase, the following cohorts will be enrolled in the Expansion Phase and treated with CORT125281 + enzalutamide according to the RD regimen. The DRC may elect to expand more than 1 dose level, if needed, to better define the RD.

- Abi-Resistant Cohort: Patients who have progressed during treatment with abiraterone and no other AR-blocking therapies (N~20)
 - Food-Effect Subcohort: The effect of food on the PK of CORT125281 will be evaluated in 10 patients enrolled to the Abi-Resistant Cohort. These 10 patients will have a 7-day Lead-In Period as follows:

- Day -7: Single oral dose of CORT125281 administered under fasting conditions
- Day 1: Single oral dose of CORT125281 administered 30 minutes after a standard breakfast. These patients will initiate enzalutamide on Cycle 1 Day 2 to avoid confounding the assessment of the effect of food on CORT125281 PK

Patients in the Abi-Resistant Cohort who do not participate in the food-effect study will not have a Lead-In Period.

- ARant-Resistant Cohort: Patients who have progressed during treatment with enzalutamide or second-generation AR-blocking therapies (N≈20). Note: Patients in the ARant-Resistant Cohort will not have a Lead-In Period.

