3.2 Number of Patients and Study Participation

3.2.1 Number of Patients

The number of patients in Dose-Determination Phase Segment 1 will depend on the number of dose cohorts assessed and the DLTs observed (6 to 9 patients per cohort).

Approximately 20 patients will be enrolled in Dose-Determination Phase Segment 2 to achieve 16 DLT-evaluable patients (Arm A: 12 patients, Arm B: 4 patients).

Approximately 40 patients will be enrolled in the Expansion Phase (20 patients in each cohort).

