2.4. Phase 2a, Expansion Phase

Once the RP2D has been determined in the Dose-Determination Phase, the following cohorts will be enrolled and treated with exicorilant + enzalutamide according to the RP2D regimen. The DRC may elect to expand more than 1 dose level, if needed, to better define the RP2D.

- **Abiraterone (Abi)-Resistant Cohort:** Patients who have progressed during treatment with abiraterone and have received no other AR-blocking therapies (N≈20)
 - **Food-Effect Subcohort:** The effect of food on the PK of exicorilant will be evaluated in 10 patients enrolled to the Abi-Resistant Cohort. These 10 patients will have a 7-day Lead-In Period as follows:
Day -7: Single oral dose of exicorilant administered under fasting conditions.
Day 1: Single oral dose of exicorilant administered 30 minutes after a standard breakfast. These patients will initiate enzalutamide on Cycle 1 Day 2 to avoid confounding the assessment of the effect of food on exicorilant PK.
Patients in the Abi-Resistant Cohort who do not participate in the food-effect study will not have a Lead-In Period.
- **AR Antagonist (ARant)-Resistant Cohort:** Patients who have progressed during treatment with enzalutamide or second-generation AR-blocking therapies (N≈20). Note: Patients in the ARant-Resistant Cohort will not have a Lead-In Period.

3. Study Objectives

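### Protocol 5.3.3 and Tables 5 and 6 fix twice-daily CORT125281 for the Expansion Phase, while the rest of the protocol and the SAP leave the regimen to a recommended dose not yet chosen

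*Protocol*

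**What the plan says.** Protocol 5.3.3 covers the two groups of Expansion patients separately:

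- **Food-Effect Subcohort:** after single doses on Day -7 and Cycle 1 Day 1, "patients will be treated with CORT125281 BID and enzalutamide QD for the remainder of the Combination Treatment Period". Table 5 shows twice-daily dosing from Cycle 1 Day 2 onward.
- **All other Expansion patients:** "These patients will initiate treatment with both CORT125281 BID and enzalutamide QD on Cycle 1 Day 1". Table 6 shows twice-daily dosing throughout.

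Elsewhere the frequency is left open:

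- Synopsis and Protocol 3.1: cohorts are "treated with CORT125281 (with the RD regimen, under fed conditions) + enzalutamide".
- Synopsis, study drug dose: "Expansion Phase: CORT125281 at the RD, as determined in the Dose-Determination Phase".
- Protocol 3.1.2: "treated with CORT125281 + enzalutamide according to the RD regimen".
- SAP 2.4: "treated with exicorilant + enzalutamide according to the RP2D regimen".

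Protocol 1.5.1 places Expansion enrolment after that choice: "Once both segments of the Dose-Determination Phase are complete, and the RD has been determined".

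**The concern.** Section 5.3.3 states a dosing frequency that every other description of the Expansion Phase leaves to the Data Review Committee (DRC). It makes no exception for a different RD, and neither document says which text governs.

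This is an operational section. Protocol 7.2 tells staff to instruct food-effect patients according to Table 5, Protocol 6 requires procedures to be carried out as described, and Protocol 11.7 restricts deviations. With a once-daily RD, a site following one text departs from the other.

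At stake is whether Expansion patients receive the regimen the phase is meant to evaluate. The PSA response rate that sizes both 20-patient cohorts (Protocol 9.4.2) would not describe the RD if patients were dosed on a different schedule, and neither would the safety results.

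**Working it through.** The plan gives no figure to reproduce here. The check compares the texts and then asks what follows under each possible RD.

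**1. Is the frequency open when 5.3.3 fixes it?** Yes. Protocol 9.4.1 has Segment 1 determine an RD for twice-daily dosing and Segment 2 an RD for once-daily dosing with food. Either remains possible.

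**2. Which is likelier?** Once daily. Protocol 1.3.2.1 plans the once-daily schedule as the step before the expansion cohorts. Protocol 5.4.2 has the DRC assess the once-daily titration as the Phase 2 RD, then moves eligible Arm B patients to the recommended upward titration. The synopsis and Protocol 3.1 specify fed dosing in Expansion. Segment 2 is the segment run with food; the Segment 1 cohorts were fasted (1.3.2.1).

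**3. What exactly conflicts?** Only the frequency. Section 5.3.3 gives no milligram dose, does not mention titration, and sets no meal rule after the food-effect doses.

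**4. How many patients?** Protocol 3.2.1 plans 20 per cohort.

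| RD chosen | Expansion patients with two stated frequencies |
|---|---|
| Once daily | up to 20 + 20 = 40 |
| Twice daily | 0 |

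**5. DLT data in this study for each schedule**

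| Schedule | DLT data |
|---|---|
| Twice daily with food | 0 patients |
| 140 mg twice daily, fasted | Cohort 2: 1 of 3; Cohort 3: 0 of 6; pooled (1 + 0)/(3 + 6) = 1/9 = 11.1% |
| Once daily with food | 16 DLT-evaluable patients planned (Segment 2) |

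Exact (Clopper-Pearson) 95% interval for 1/9:

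- lower limit = Beta quantile(0.025; 1, 9) = 0.0028
- upper limit = Beta quantile(0.975; 2, 8) = 0.4825

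The interval is 0.3% to 48.2%. The denominator of 9 assumes that all three Cohort 2 patients were DLT-evaluable, which 1.3.2.1 does not state. If only the patient with the DLT was evaluable, the figure would be 1/(1 + 6) = 14.3%. The pooling also combines a cohort with an enzalutamide lead-in and one without.

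**6. Is a twice-daily RD practical?** 180 mg twice daily was deemed intolerable, so 140 mg is the only twice-daily dose considered tolerable.

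- Daily dose: 140 × 2 = 280 mg, inside the 240 to 320 mg once-daily range, so the two candidate regimens do not differ materially in daily dose.
- Hard-shell capsules: 2 × 60 + 20 = 140 mg.
- Softgels: 140/40 = 3.5 capsules.

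A 140 mg twice-daily RD is therefore possible but would need continued hard-shell supply. Table 1 moves only existing patients to softgels and does not say that hard-shell supply ends.

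**7. What would a misdosed patient take?** Section 5.3.3 does not say whether a once-daily RD would be repeated or divided. As an illustration only, repeating it would give 240 × 2 = 480 to 320 × 2 = 640 mg/day. The intolerable Segment 1 dose was 180 × 2 = 360 mg/day, but it was fasted and in a different capsule, so this is not a like-for-like comparison.

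**The case against.** The strongest reply is that harm needs several things to go wrong together. The RD must be once daily, 5.3.3 must survive unchanged until Expansion opens, and a site must follow it over the RD. No site can dose from 5.3.3 alone, because it has no milligram dose. The protocol ties each RD to a schedule, so anyone looking up the dose should also see the frequency.

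There are safeguards as well: DRC review at least every 6 months, a stopping rule if the DLT rate exceeds 33%, and an interim safety analysis after 20 Expansion patients complete 3 cycles. In Study CORT125281-600, food lowered Cmax by about 47% with similar AUC (3 subjects, single dose), which tempers the concern about fed twice-daily dosing, although receptor antagonism was stronger with food.

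Much of this stands. The harm is conditional, and 1/9 describes fasted 140 mg twice daily, not the effect of the conflict. A twice-daily RD given with food would also lack DLT data without any textual conflict; that is a separate bridging question.

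It does not remove the contradiction. The safeguards may detect toxicity but do not settle which frequency is correct. The DLT-evaluation period in Protocol 5.5 is defined only for Segments 1 and 2, and SAP 8.7 defines expected dose only for those segments.

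**Conclusion.** The concern holds. Protocol 5.3.3 and Tables 5 and 6 contradict the synopsis, Protocol 3.1 and 3.1.2, and SAP 2.4 on dosing frequency, and nothing resolves the conflict. This is an inconsistency in the text, not a disagreement with a design decision.

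Its reach depends on the RD: none of the Expansion patients if it is twice daily, up to about 40 if it is once daily. Misdosing further assumes that 5.3.3 is left as it is and followed in preference to the RD. For the Food-Effect Subcohort the conflict starts on Cycle 1 Day 2, because the Day -7 and Day 1 single doses are not in dispute. It should be fixed before Expansion opens.

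**What to change.** In 5.3.3 replace BID, and in Tables 5 and 6 replace the twice-a-day entries for CORT125281, with: *per the DRC-determined RD regimen (frequency, any titration, with food)*. Keep the Food-Effect Subcohort's single doses on Day -7 and Day 1. This wording is correct whichever RD is chosen.

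Only if the RD is once daily with the evening meal, also align Table 22. It samples around a morning dose on Cycle 2 Day 1 and Cycle 3 Day 1, whereas the Segment 2 rule in 5.3.2 puts all doses after Cycle 2 in the evening. If that rule carries over, extend its morning-dose exception (at least 18 hours since the previous dose) to Expansion and make it cover Cycle 3 Day 1.

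The cost is wording only, with no added patients or visits. SAP 2.4 needs no change. An Expansion entry for expected dose in SAP 8.7 would be a sensible addition at the same time.
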